3.2 Investigational Product (treatment, device) and Indication

The teaching of physician-patient communication as proposed by the Swiss Academy of Medical Sciences postulates that « *the transmission of information is intended to inform the patient in such a way that he/she is able to correctly assess the diagnosis, the type of intervention, its course, its purpose, its usefulness and the risks associated with it* » (ASSM, 2013). No details are given on how to deliver information about a painful procedure, let alone on how to limit its painful and anxious impact. The issues surrounding patients' informed consent (Wells et al., 2012) and the elements to be disclosed during the conduct of a procedure are debated and researched, the issue being that it is essential to use precise and detailed vocabulary in order to obtain informed consent. Nevertheless, more positive or less explicit words could be used in the procedure itself (Lang et al., 2005). In addition, caregivers often confuse the consent phase (before initiating the procedure) and the description phase of the procedure while it is in progress (« procedural disclosure » - procedural information) which is not mandatory and not necessarily helpful (Krauss, 2015). Lang proposes to separate these two phases temporally. Thus, the elements necessary to be able to base informed consent (technical characteristics, adverse reactions, etc.) should be detailed before the procedure, whereas during the procedure only open-ended questions (« What do you feel? »), neutral statements or positive suggestions should be used (Lang et al., 2005). This study focuses only on procedural information relating to the placement of the PIC, the co-investigators intervening only after the information on which informed consent is based has been provided. The purpose of the intervention is then to modulate this specific procedural information given to patients when a PIC is placed in the Emergency Department.

The primary objective of this study is thus to compare the effect on painful feelings induced by the insertion of a PIC in the ED: 1) by two different ways of communicating information; 2) by two different vectors of the message. To achieve the first objective, the study will compare the effect of a usual message to prepare patients for the painful stimulus during PIC insertion with the effect generated by a message with positive content. The latter will not contain explicit words such as « pain, sting, needle », but instead words suggesting specific notions of control and comfort related to the procedure. The main objective of this study is thus to determine whether the use of positive language during the insertion of a PIC in the ED improves patients' pain experience compared to usual language practices. As for the second objective, the effect of the message vector, it will be studied by testing if the effect of this positive language is comparable, whether the message is delivered by a standardized audio recording or directly by the caregiver performing the procedure.

Secondarily, this study aims to explore the effect of the intervention on patients' anxiety. Finally, it

seeks to explore the differences that may exist between an assessment of pain and anxiety made by patients (feelings of pain and anxiety) and that made by caregivers (estimated pain and anxiety) as well as the possible determinants of these differences, if they exist (patients: sex, age, origin, level of education / caregivers: sex, age).

3.3 Preclinical Evidence

Non-applicable.

3.4 Clinical Evidence to Date

A systematic review, including a meta-analysis of 51 studies (5,079 patients) was conducted in 2015 about the effect of patient-caregiver communication on pain (Mistiaen et al., 2016). Because interventions on communication can be very diverse, this review classified the interventions of the different studies into three categories: cognitive, emotional and procedural interventions. In the sense of this systematic review, our intervention is part of cognitive interventions, seeking to elicit negative/neutral/positive expectations in patients, and of procedural interventions, seeking to prepare patients for an invasive procedure. Particularly in procedural interventions, our intervention consists in the transmission of procedural information (description of events: what, when and how) and sensory (description of the sensory aspects of the procedure) as well as behavioural instruction (explain to patients what they should do in order to facilitate the procedure). With respect to cognitive interventions, 13 of the 19 studies included in the review found significant differences between groups with a general tendency to reduce pain for groups with positive or neutral suggestion versus those with negative suggestion or control. Of the 6 randomized controlled studies that had applied cognitive interventions to acute pain and measured pain intensity, 2 studies reported that positive suggestions reduced pain and 2 studies reported that negative suggestions increased pain, with the last 2 studies finding no effect on both. According to this systematic review, negative suggestions would thus increase the painful feelings while positive suggestions would reduce them, but the extent of the effect is not clear and the overall quality of the studies was low. Concerning the transmission of procedural and sensory information, alone or in combination with other procedural interventions such as behavioural instruction, they tend to lead to a reduction in pain, although the amount of information required is uncertain and a possible excess of information is harmful. Finally, the systematic review concludes that educating patients in an empathetic and positive way reduces their painful symptomatology. However, we note that none of the studies included in the systematic review were carried out in Switzerland, which may have its own peculiarities in terms of pain feelings, expression and evaluation of pain.

3.5 Dose Rationale / Medical Device: Rationale for the intended purpose in study (pre-market MD)

Non-applicable.

3.6 Explanation for choice of comparator (or placebo)

In this study, we chose to compare a message content commonly used in invasive medical procedures with a message content that is positive. While it may be useful to create a « no communication » group to position the two messages in relation to each other, total silence on the part of caregivers when placing the PIC may be poorly perceived by patients and caregivers. This would be an intervention well beyond the usual practice and difficult to ask from caregivers.

The control message was developed based on the literature (Varelmann et al., 2010; Dutt-Gupta et al., 2007; Lang et al., 2005; etc.) and clinical practices identified during an observation day in the LUH ED conducted to assess the practicality of this study. The content of these messages is detailed in section 8 « Study intervention ».

3.7 Risks / Benefits

No specific risk is expected for this very brief intervention, only modulating a procedural information. Should any adverse event occur as a result of the intervention, it will be spontaneously reported in the CRF by the co-investigators during the intervention and, if necessary, forwarded to the CEC. Investigators are available to participants during and after the study (as it is mentioned in the full information sheet).

An observation day at the LUH ED was conducted in order to assess the practical feasibility of this study and to minimize disruption to the caregivers' work. This will allow most of the data to be

collected before and after the insertion of the PIC, without interfering with caregivers' work.

In addition, the listening device will be systematically disinfected by co-investigators after use. By default, an earphone device will be made available to patients. In the event of refusal, unsuitable morphology or wearing a hearing aid, a headphone device may be provided.

If this study is able to demonstrate that positive communication during a PIC insertion effectively reduces patients' pain and anxiety, it will be a simple teachable intervention that can be easily transposed into current clinical practice and could improve management of the PIC insertion, a very common practice in EDs. If this message can also be delivered by audio recording, with good effects, such communication could be considered for procedures known to be painful or anxious. Indeed, if the study demonstrates a reduction in pain and anxiety, it would indicate a new approach to multimodal pain management in EDs. These results would therefore not only have the potential to change the practice of caregivers during painful procedures in emergencies, but also to encourage the integration of these notions of communication in their training. This study would also contribute to a better understanding of the placebo and nocebo effects of communication and help improve caregiver-patient communication.

3.8 Justification of choice of study population

The population targeted by this study includes medically stable patients in the ED whose management requires the insertion of a CIP. This medical procedure is performed daily in the ED without prior analgesia. Initiating a reflection on how to reduce its painful and anxious impact is therefore relevant and necessary. It is also easier to carry out this type of study in the ED because the necessary number of patients is guaranteed.

Patients who are clinically unstable, incapable of decision-making or with whom it is difficult to communicate are excluded. Thus, this study does not target a vulnerable population, although these are emergency situations. Moreover, patients will be able to reconsider their decision to participate in the study at any time and will be given a minimum of 15 minutes to complete the data collection process before signing the consent form. Since the medical management of patients is independent of the study, the emergency physician responsible for the patient may also decide to withdraw him/her from the study in order to safeguard his/her interests and provide appropriate management.

4. STUDY OBJECTIVES

4.1 Overall Objective

The overall objective of this study is to investigate if the modulation of the information when inserting a PIC in the ED has an impact on patients' pain and anxiety levels and if this effect is comparable, whether the message is delivered through a standardized audio recording or directly by caregivers. It also explores if there are differences in patients' and caregivers' assessments of pain and anxiety.

4.2 Primary Objective

The primary objective of this study is to determine if the use of a positive information, avoiding negative words and suggesting specific notions of control and comfort related to the procedure, when inserting a PIC in the ED, reduces pain intensity when compared to the usual language practices.

The primary objective is also to determine if this effect is comparable, whether the message is delivered by a standardized audio recording or by the caregiver performing the procedure.

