Background and Rationale:	The occurrence of a medical or surgical emergency is a stressful life event. An Emergency Department (ED) is also a noisy and sometimes chaotic environment, contributing in itself to increase anxiety associated with the reason for consultation. Some common medical procedures, such as PIC insertion, can not only induce pain, but can also exacerbate anxiety or pre-existing pain. Nevertheless, the well-being of patients, especially during invasive medical procedures, can be improved by various communication techniques. However, the literature and clinical observation have shown that negative words are traditionally used to warn patients of an impending painful stimuli. Though, in contrary to common beliefs and practices, this type of warning can increase their pain and anxiety. Using words with negative emotional content has even a greater aggravating impact than the positive impact of using words with positive emotional content. However, the studies that explored the impact of such messages have two limitations: they were not conducted in the ED context, and the effect attributable to caregivers themselves was little studied. Also, caregivers who deliver a message with positive or negative content in the context of a study are aware of this message and therefore are not blinded to the intervention arm. Thus, this absence of a double-blind study introduces the possibility of a bias, i.e. that the benefit of a positive message can be mediated by the caregivers and caregiver-patient interaction in a more global aspect and not simply by the verbal content of the message. It is indeed possible that caregivers, more or less consciously, may add additional elements in their communication that are congruent with the message studied, whether in the field of verbal or non-verbal communication (voice tone, warmth, empathy, etc.).

Objective(s):	The purpose of this study is to investigate whether the modulation of an information regarding a PIC insertion in the ED has an impact on patients' pain and anxiety levels. It also aims to determine if this effect is comparable, whether the message is delivered through a standardized audio recording or directly by caregivers. Finally, it aims to explore whether there are differences in patients' and caregivers' assessments of pain and anxiety.

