4.3 Secondary Objectives

Secondarily, this study aims to explore the effect of the intervention on patients' anxiety.

Finally, it seeks to explore the differences that may exist between an assessment of pain and anxiety made by patients (feelings of pain and anxiety) and that made by caregivers (estimated pain and anxiety) as well as the possible determinants of these differences, if they exist (patients: sex, age, origin, level of education / caregivers: sex, age).

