11.1 Hypothesis

First null hypothesis: The recorded intervention message has an effect comparable to that of the recorded control message on the painful feeling induced by the insertion of a PIC.

First alternative hypothesis: The recorded intervention message reduces the intensity and unpleasantness of the pain induced by a PIC insertion of at least 13 mm from the recorded control message.

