11.2 Determination of Sample Size

Based on a review of studies on pain during a PIC insertion (Baxter et al., 2009; Dutt-Gupta et al., 2007; Fossum et al., 2016; Fry et al., 2001; Hartstein et al., 2008; Kim et al., 2012; Marco et al., 2007; Ott et al., 2007), 2012; Soysal et al., 2005; Speirs et al., 2001; Witting et al., 2016), the mean pain intensity is estimated at 34 mm by the Visual Analog Scale (with a possible intensity between 0 and 100 mm), with a standard deviation estimated at 24 mm. To detect the smallest decrease in clinically significant pain intensity of 13 mm (Todd et al., 1996) due to the intervention, a sample of 110 patients, or 55 patients per arm, is required, with a power set at 80% and alpha set at 5%. Taking into account missing values or refusal to participate after randomization estimated at 10% of patients, 60 patients will be randomized per arm. A total of at least 240 patients will therefore be recruited for the two phases, i.e. the four arms, of the study.

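### Comparability of audio and caregiver delivery is part of the primary objective, but Section 11 gives no between-phase contrast or reading rule; the difference between phase effects would have a 95% half-width of about 12.7 mm

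*Combined protocol and SAP*

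**What the plan says.** **Objectives.** Section 4.2 first names the message comparison and then adds: "The primary objective is also to determine if this effect is comparable, whether the message is delivered by a standardized audio recording" (the alternative being the caregiver who does the procedure). Section 3.2 describes the primary objective as comparing effects on pain "1) by two different ways of communicating information; 2) by two different vectors of the message", and says of the vector that "it will be studied by testing if the effect of this positive language is comparable". The same section then calls message content the main objective and the vector the second one. Section 4.1 ("if this effect is comparable, whether the message is delivered through a standardized audio recording or directly by caregivers") and the Synopsis under Objective(s) ("It also aims to determine if this effect is comparable, whether the message is delivered through a standardized audio recording or directly by caregivers") repeat the aim without calling it primary. Section 4.3 opens with anxiety ("Secondarily, this study aims to explore the effect of the intervention on patients' anxiety") and does not list the vector.

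**Hypothesis and size.** Section 11.1 holds one null and one alternative, each labelled as the first. The alternative is "The recorded intervention message reduces the intensity and unpleasantness of the pain induced by a PIC insertion of at least 13 mm" relative to the recorded control. No second pair follows. Section 11.2 and the Synopsis (Statistical Considerations) derive 55 patients per arm for a two-arm comparison, raise this to 60, and double it: "A total of at least 240 patients will therefore be recruited for the two phases, i.e. the four arms, of the study".

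**Analysis.** Sections 11.4 to 11.4.3 plan a t-test or a Wilcoxon rank sum test between randomised groups, by intention to treat and then in patients who received the full message. Section 9.2.1 allows an optional analysis by caregiver, using a study number recorded only in the second phase. Section 6.1 explains that the phases run one after the other for organisational reasons.

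**The concern.** Patients are randomised to a message within a phase, not to a vector. Asking whether the message effect is the same by audio and by caregiver means comparing two effects, each estimated in a different phase. Nothing in Section 11 defines that contrast or says what result would count as comparable.

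Following the plan literally gives two separate within-phase tests. Two significant results would not show that the effects are alike, and one significant with one non-significant result would not show that they differ. The analyst would have to choose the contrast, and the meaning of comparable, after seeing the data. The question also matters to the rationale. Section 3.1 asks whether a benefit comes from the caregiver rather than from the words, and Section 3.7 ties possible use of recordings to their effect.

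**Working it through.** **Inputs (Section 11.2).** Target 13 mm, SD 24 mm, alpha 0.05, power 80%, 55 evaluable and 60 randomised per arm, four arms. Sidedness is not stated.

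**1. The plan's own figure.** For two means, n per arm = 2 × [(1.960 + 0.842) × 24 / 13]² = 53.5, so 54 by the normal formula. The t-based solution is 54.48, so 55. The stated 55 is reproduced with a two-sided test; a one-sided test gives 43. At 55 per arm, power within a phase is about 80% (t-based).

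**2. Precision within one phase.** SE = 24 × √(2/55) = 4.58 mm; 95% half-width = 1.96 × 4.58 = 9.0 mm.

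**3. Precision of the difference between phase effects.** The contrast is (intervention − control) in phase 2 minus (intervention − control) in phase 1, so four arm means enter. SE = 24 × √(4/n).

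| Evaluable per arm | SE (mm) | 95% half-width (mm) |
|---|---|---|
| 54 (60 less 10%) | 6.53 | 12.8 |
| 55 | 6.47 | 12.7 |
| 60 (no losses) | 6.20 | 12.1 |

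An observed difference of exactly zero at 55 per arm would give an interval of about −12.7 to +12.7 mm.

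**4. Power to detect a difference in effects (two-sided 0.05, 55 per arm).** For a true 13 mm difference: Φ(13/6.47 − 1.96) = Φ(0.05) = 0.52. Detectable with 80% power: 2.802 × 6.47 = 18.1 mm.

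**5. Power to conclude comparability.** The documents give no margin. Assume 13 mm, truly equal effects, and a 90% CI that must lie inside ±13 mm. Power = 2 × Φ(13/6.47 − 1.645) − 1 = 2 × Φ(0.36) − 1 = 0.28. For 80% power on the same assumptions, n per arm = 4 × [(1.645 + 1.282) × 24 / 13]² = 116.8, so 117.

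**6. Sensitivity at 55 per arm (assumed ranges).**
- SD 20 mm: SE 5.39, half-width 10.6 mm, power for a 13 mm difference Φ(13/5.39 − 1.96) = 0.67.
- SD 28 mm: SE 7.55, half-width 14.8 mm, power Φ(13/7.55 − 1.96) = 0.41.
- Phase 2 caregiver design effect D of 1.2 to 1.5 at SD 24 mm: half-width = 1.96 × 24 × √(2/55 + 2D/55) = 13.3 to 14.2 mm.
- Adjustment for baseline VAS would work the other way, by an amount the documents do not give.

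**The case against.** **The primary label is not uniform.** Only Sections 3.2 and 4.2 use it. Section 3.2 itself ranks message content first, and the introduction to Section 11 states the statistical aim as superiority of the positive message. This stands, and part of the defect is inconsistent labelling. But Section 4.2 is the formal statement of the primary objective, and the vector appears nowhere as secondary.

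**Other text might fill the gap.** It does not. The caregiver analysis in Section 9.2.1 is optional and confined to phase 2. The per-protocol analysis in 11.4.1 concerns incomplete messages in phase 2. Section 11.4.6 covers reporting of deviations, and there is no planned contrast to deviate from.

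**The sequential design is disclosed and justified.** True. That explains why phase is not randomised, but it does not supply an analysis.

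**Stronger readings that the documents do not support.** A reader might infer that the planned size could never support comparability. With an assumed 13 mm margin, an observed zero difference would in fact pass, since the 90% half-width is 1.645 × 6.47 = 10.6 mm; the result is unlikely, not impossible. A reader might also take 13 mm as the plan's margin, but Section 11.2 uses it as the smallest clinically significant decrease in pain, not as a tolerable difference between two effects. Finally, the exclusion for prior knowledge of the assigned message looks like a phase 1-only difference in Section 7.1 and the Synopsis, but Section 7.4 states it without a phase limit, so it cannot be counted as one until these are reconciled.

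**Conclusion.** The point holds. A question placed within the primary objective has no hypothesis, contrast or reading rule, and the plan as written does not answer it. The within-phase superiority tests, with a half-width of 9.0 mm and about 80% power each, are unaffected; the 12.7 mm figure belongs only to the difference between the two phase effects.

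That difference can be estimated from data already planned, but imprecisely: about 52% power for a 13 mm difference, 18 mm detectable with 80% power, and about 28% power for equivalence on an assumed 13 mm margin. The planned size is therefore unlikely to support a conclusion of comparability. These figures assume an SD of 24 mm in all four arms, 55 evaluable patients per arm, no baseline adjustment and no clustering. Because phase is not randomised, a larger sample alone would not make the contrast a clean comparison of vectors.

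**What to change.** 1. In 11.4.3, pre-specify one model for pain intensity over both phases, with message, phase, message × phase and baseline VAS. Report the interaction in mm with its 95% CI, whether or not the VAS is Gaussian. Allow for caregiver clustering in phase 2 through the study number, and note that the current plan records no caregiver number in phase 1.
2. State that neither a non-significant interaction nor similar or differing phase-wise p-values will be read as showing comparability or a difference.
3. In 3.2 and 4.2/4.3, label the vector comparison as a secondary or exploratory, non-randomised estimate. Section 4.1 and the Synopsis objectives need only matching wording.
4. In 11.2 and the Synopsis (Statistical Considerations), state the expected unadjusted precision of about ±13 mm for the difference between phase effects, which baseline adjustment may narrow and clustering may widen.
5. Optional: in the Synopsis (Measurements and procedures) and the Study Schedule, qualify the claim that the phases differ only in the vector. Name calendar time, co-investigator blinding (6.2.2) and the caregiver-formulated message variants allowed in phase 2 (8.1.1). Reconcile Section 7.1 and the Synopsis criteria with Section 7.4 before citing the prior-knowledge exclusion as a phase difference.

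**Cost.** One extra model on data already collected, some wording, and a more modest claim about the vector; no extra patients or visits. Keeping the comparison primary would instead need a justified margin and a larger sample: 117 evaluable per arm on the assumed 13 mm margin, before any allowance for losses.
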